##### **Growth Modulation Index (GMI)**

GMI is the ratio between time to progression (TTP) with pazopanib (TTPp) divided by the

TTPp-1 with the previous line of therapy.

### **Safety profile (according CTCAE, version 4.0)**

The safety and tolerability of Pazopanib will be determined by means of type, incidence, severity, timing, seriousness, and relatedness; of reported AEs, physical examinations, and laboratory tests. Toxicity will be graded and tabulated by the NCI-CTCAE v 4.0.

### **10.2. Efficacy assessment**

Disease should be captured and target/non-target identified at baseline by CT or MRI as appropriate. Subsequently, imaging studies required to investigate known disease should be performed on week 6/7, on week 12 and every 8 weeks thereafter. Imaging methods will be employed consistently during the course of each patient's evaluation during the study. After discontinuation of protocol treatment, patients who have not progressed will still be re-evaluated every 8 weeks, unless they have started a new anti-cancer therapy, withdrawal of consent or death, whichever occur first. 10.2.1. Efficacy assessment populations:

Intent to treat (ITT) analysis: Efficacy analysis will be carried out in the ITT population. All patients participating in the study will be included in the analysis of efficacy.

Per Protocol (PP) analysis: Efficacy analysis will be carried out in per protocol population. All patients participating in the study and received at least 3 weeks of treatment with Pazopanib with no major protocol deviations will be included in the analysis of efficacy.

### **10.3. Safety assessment**

Any patient included in the study receiving at least a single dose of study medication will be evaluable for the toxicity analysis.

Safety profile will be characterized by treatment-emergent Adverse Events (TEAE), vital signs and laboratory abnormalities. Assessment of adverse events will include type, incidence, severity (graded by the National Cancer Institute [NCI] Common Terminology Criteria for Adverse Events [CTCAE], Version 4.0), timing, seriousness, and relatedness; and laboratory abnormalities. Baseline tumor-related signs and symptoms will be recorded as adverse events during the trial if they worsen in severity or increase in frequency.

In each study visit all adverse events will be registered according to NCI-CTC version 4.0

### **10.4. Sample Size and Statistical analysis**

The drug will be separately investigated in the following liposarcoma subtypes:

- Well-differentiated liposarcoma/dedifferentiated liposarcoma (ALT-WD)
- Myxoid/round cell liposarcoma.

The Simon two-stage design will be separately applied in each stratum. A total of 17 patients will be included in each stratum for the first step of the trial. For the second step, 20 (up to 37) additional patients will enter in each stratum provided the results of the first step were positive. A total of 37 patients could enter the study in each stratum.

Success will be defined as documented disease stabilization or response after at least 12 weeks of therapy.

The following design characteristics and decision rules apply separately to each stratum. The Simon optimal one sample two stages testing procedure (optimal design) will be used with the following hypotheses:

- Success in 20% of the cases or less in one of the strata will be considered as unacceptable, and would not warrant further investigation (null hypothesis). Therefore, the value of P0 will be taken as 20%.
- Success in 40% of the cases or more in one of the strata will be considered as an acceptable result warranting further investigation of the drug in this histology (alternative hypothesis). Therefore, the value of P1 will be taken as 40%.

These two reference values are based on a retrospective analysis of the EORTC STBSG database of patients treated with 2nd line therapy.

Under those hypotheses, a total of 37 eligible and treated patients will need to be recruited in each stratum and followed for at least 12 weeks. The size of the type I and type II errors is 10% ( $\alpha=\beta=0.1$ ).

A total of 17 eligible and treated patients will be included (in each stratum) in the first step of the study.

1. If  $\leq 3$  successes are observed in a stratum, the trial will be stopped in this stratum with the conclusion that the drug should not be further investigated in this histology.
2. Else, patients will continue to be accrued until 37 eligible patients have been recruited and have started therapy. If 11 or more successes are observed in those 37 patients, we will conclude that the results of this trial warrant further investigation in this histology.

In addition, sequential tests for each cohort combined with overall futility test will be performed after the first stage accrual is achieved, as described by LeBlanc et al. This procedure allows for stopping a subgroup for futility keeping error rates.

PFS and OS will be calculated from the date of treatment initiation and will be estimated by the Kaplan-Meier method in each stratum. Due to the rarity of the disease, patients will be allowed to get in the study while the first stage analysis is being performed unless otherwise advised by safety or futility sequential test for each cohort.

## **11. LEGAL AND ETHICS CONSIDERATION**

### **11.1. Ethic Committee**

This study will be conducted in accordance with the ethical principles that have their origin in the Declaration of Helsinki adopted by the 18th World Medical Association General Assembly, Helsinki, Finland.

The study will be carried out in conformity with the requirements of the “Declaration of Helsinki” adopted by the 18th World Medical Association General Assembly held in Helsinki, Finland, June 1964 and revised by the 29th World Medical Association General Assembly held in October 1975 in Tokyo, the 35th World Medical Association General Assembly held in Venice in October 1983, the 41st World Medical Association General Assembly celebrated in Hong Kong in 1989, the 48th World Medical Association General Assembly held in Somerset West, South Africa in October 1996, the 52nd World Medical Association General Assembly celebrated in Edinburgh, Scotland in October 2000, the 59th World Medical Association General Assembly held in Seoul, Korea, October 2008 (Annex XII); the Good Clinical Practice (GCP) norms issued by the working group on the Efficacy of Medicinal Substances of the European Union (1990) (CPMP/ICH/135/95) and applicable regulatory requirements and laws on the country where the Trial is taking place. According to Directive 95/46 of the European parliament and 2001/20 /EC by which the requirements to perform a clinical trial are established, the information obtained in the course of the clinical trial, will only be able to be used by the clinical trial sponsor to evaluate the results according to the mentioned regulation.

### **11.2. Authorities**

The study protocol and/or related documents will be submitted to regulatory authorities before commencement of the clinical trial, as national authorities on the country where the trial is taking place require.

### **11.3. Informed consent**

The patient should sign 2 separate informed consents: one for the clinical trial and another for biological samples studies.

The clinician will have to explain the nature, objectives and possible consequences of the clinical trial in a manner that is understandable by the patient.

The patient must give his/her consent before being admitted into the study and before biological samples are taken.

The study subject will provide his/her consent, signing by duplicate the appropriate model. For this purpose, each model must carry the signature of investigator and patient. The investigator will retain one copy of the original of each patient's signed consent form.

The investigator will not start any investigation related with the study until the consent has been obtained.

The informed consent form used in this study, and any changes made during the course of the study, must be prospectively approved by the Ethics Committee.

### **11.4. Confidentiality**

In order to warrant the confidentiality of study data according to Directive 95/46 of the European parliament and 2001/20/EC, personal and clinical data can only be accessed by

the Sponsor of the study or its designated staff, for monitoring/auditing purposes, the investigator and team of collaborators, the Ethics Committee of the investigational site, or the one overseeing the centre, and pertinent Health Authorities.

The investigator should facilitate access to the source documents and data for monitoring and auditing purposes.

The content of the case report forms (CRF), as well as the documents generated during the study will be protected from non permitted uses by persons not involved in the investigation, and will therefore be considered strictly confidential and not revealed to third parties, except those specified in the previous paragraphs.

### ***11.5. Insurance Policy***

The insurance or indemnity in accordance with pertinent regulatory requirements will be provided.

All patients in this study are insured through the Insurance Company HDI International with an insurance policy that satisfies the conditions stipulated by the RD 223/2004 in Spain.

### ***11.6. End of the study***

The study will be considered closed from a normative point of view after data on primary and secondary variables are sufficiently prepared for its initial publication.

### ***11.7. Early study termination***

This study can be terminated prematurely if in the opinion of the sponsor there is a reasonable and sufficient cause. The investigator will receive a written notification in which the sponsor motivates the interruption of the study. Reasons that justify are as follows, but not limited to:

- Finding of unforeseen, considerable or unacceptable risks for the patients.
- Impossibility to include an acceptable number of patients.
- Insufficient compliance with protocol requisites.
- Plans to modify halt or discontinue the development of study drug.
- In case of early termination of the study, all the study material (blank or totally or partially filled out CRF, study drugs, etc) must be returned to GEIS.

## **12. PRACTICAL CONSIDERATIONS**

### ***12.1. Diagnostic Criteria for the Study Disease***

Patients included on this trial should have histological confirmed diagnosis of high or intermediate grade malignant liposarcoma with metastatic or locally advanced disease. Patient must have documentation of disease progression within 6 months prior to study entry documented as progressive by CT scan or MRI. Prior scans will be used to classify the patient as having progressive disease at baseline according to RECIST 1.1 criteria.

Paraffin embedded tumour blocks/slides will be collected for all patients for a central pathological review. First diagnosis sample or another more recent available sample obtained during the routine care previous to study entry will be acceptable. Tumour biopsy at study entry will NOT be compulsory but recommended if clinically acceptable (ex. superficial or easily accessible locations). The central pathological review is a pre-requisite for entering the trial; the study treatment should not be initiated unless the diagnosis is confirmed by means of the central pathological review.

### ***12.2. Responsibilities according to Good Clinical Practice***

#### **Investigator Responsibilities**

Responsibilities of the principal investigator of each participating centre include:

- To sign the study protocol.
- To know in depth all study drugs characteristics.
- To obtain informed consent of subjects before inclusion in the trial.
- To ensure that adequate medical care is provided to a subject for any adverse events, including clinically significant laboratory valued, related to the trial.
- Collect, register and notify data in a correct way.
- To notify immediately to the sponsor all SAE and unexpected adverse events.
- To take responsibility that all people involved in the trial will respect the confidentiality of any information about the study subjects.
- To keep the Ethics Committee regularly informed on the facts of the study.
- To take responsibility on the elaboration of the final study report, providing his/her agreement and signature.

For German Investigator Responsibilities see also Annex VII

### ***12.3. Instructions for e-CRF completion***

The data will be recorded GCP-compliantly by means of the electronic documentation system (electronic CRFs) at the study centre.

The application is designed to be entirely server-based. All stages in the processing, with the exception of the actual data entry and display, are performed centrally on a web/database server. In particular, data storage will be undertaken exclusively centrally. The server is housed at "Centro de Proceso de Datos de InterHost en Madrid, [name]"

For data entry and print-outs, the system is based fully on the so-called "web interface", i.e. entry forms and reports are displayed on the client computer as HTML pages (Hyper Text Markup Language = standard page description language on the Internet) within a Web browser. No user-specific software is necessary to operate the system on the investigator's client computer. There is the possibility of direct access to the raw data by means of ODBC for further processing of the data.

The data are checked for correctness by ranks and validity and consistency checks. Implausible or missing data can be corrected or supplemented following discussion with the investigator. The correction documents are stored (audit trail).

Other than the investigator, only expressly authorised persons trained for the study may complete the e-CRF.

All data in the e-CRF should be able to be documented in measurement records or by entry in patient records.

#### **12.4. Supply of Study Drugs**

Pazopanib will be supplied by the Sponsor.

#### **12.5. Packaging and labelling**

The study drugs labels will contain all the information to comply with standing regulatory requirements.

#### **12.6. Final report and Publications**

##### **12.6.1. Clinical Trial Publication**

The final publication of the trial results will be written by the Chief Investigator on the basis of the final analysis performed at the [REDACTED]

A draft manuscript will be submitted by the Chief Investigator, other co-authors (including the Clinical Study Coordinator in Germany) and [REDACTED] for review no later than six months after receiving the Data Center report (final analysis). After revision by the Data Center, other co- authors (including the Clinical Study Coordinator in Germany) and [REDACTED], the manuscript will be sent to a major scientific journal. Results obtained in the different strata may be separately published.

Regarding authorship, institutional entry of 5% of evaluable patients in the study results in qualification for one authorship (two names for 20% entry, up to the number of authors allowed by the journal). The reference pathologist, radiologist and statistician, who have contributed to the trial, will be included in the authorship of the final manuscript.

The sequence of the authors in publication will be: Chief investigator (first), subsequent authors according to the number of patients, Clinical Study Coordinator in Germany (last).

The title of all manuscripts will include [REDACTED], and all manuscripts will include an appropriate acknowledgement section, mentioning all investigators who have contributed to the trial, the data centre staff involved in the study, as well as supporting bodies (Sponsor's Partner, etc...).

All publications (papers, abstracts, presentations...) including data from the present trial will be submitted for review to all co-authors prior to submission. They will also be submitted to [REDACTED] allowing a period of at least 30 days for review (at least 5 working days for abstracts). They will not include either [REDACTED] confidential information other than the study results or personal data on any patient, such as name or initials.

The Chief Investigator and the Clinical Study Coordinator in Germany must approve all publications, abstracts and presentations of data pertaining to patients included in this

study.

This is applicable to any individual patient registered/randomized in the trial, or any subgroup of these.

Such a publication cannot include any analysis of any of the study end-points unless the final results of the trial have already been published by the Chief Investigator.

### **12.6.2. Translational Research Publication**

Results of the translational research project will be published in major scientific journals, after the publication of the main results of the clinical study.

The first author will be the Translational Study Coordinator. All centres that have contributed to at least 5% of the analysed material will be represented in the publication by one co-author; centres that have contributed to at least 15% of the analysed material will be represented by two co-authors; this(these) author(s) will be selected by each centre internally (pathologist, molecular biologist, clinician...). All centres that have provided material for the analysis will be acknowledged. The list of authors will also include the Chief Investigator and the Clinical Study Coordinator in Germany.

The clinical trial will be registered in "clinicaltrials.gov", database of National Institute of Health of United States of America.

### **12.7. Monitoring**

The study will be monitored by regular site visits, telephone calls and periodic inspection of the CRF with enough frequency to ascertain the following:

- Investigational Products (IPs): storage conditions, that the supplies are sufficient throughout the trial.
- Rate of patient inclusion.
- Compliance with approved protocol and all approved amendment, if any.
- That the investigator receives all documents and all trial supplies needed to conduct the trial properly and to comply with the applicable regulatory regulations.
- That the investigator and trial staff is adequately informed about the trial.
- Integrity and accuracy of data (as per monitoring plan):
  - Consent Informed (version, signature and date)
  - Eligibility criteria
  - Baseline tests
  - SAE and SAE reporting
  - Primary endpoint
  - Biological Samples storage and collection
  - Stock reconciliation in pharmacy.
- CRFs completion and adverse events collection.
- Reporting of protocol deviations according GCPs and the applicable regulatory local requirements. Taking appropriate action to prevent recurrence to the detected deviations.

Monitoring visits will be done by study monitors. It is understood that these monitors will have access to the clinical records after asking the investigator. Adequate time for these visits should be allocated by the Investigator. The Investigator will also ensure that the

monitor is given direct access to the documents.

## **12.8. Protocol Amendments**

Supplements and changes to the protocol can be performed exclusively by the Sponsor, who must submit them to the Ethics Committee and the local Regulatory Authority protocol amendments.

### **12.8.1 Amendment 1**

The 1st amendment modify the schedule in the monitoring of plasma hepatotoxicity and therefore in the schedule of visits. It does not increase the number of visits. These modifications are implemented in Protocol version 2.0 April 8, 2013.

### **12.8.1 Amendment 4**

New safety information about pazopanib is included in the protocol version 3.0 February 11, 2015.

## **12.9. Data Handling**

All data (personal, clinical, economic, derived from biologic material) obtained from patients will be handled according to the Directive 95/46/EC of the European Parliament and of the Council of 24 October 1995 on the protection of individuals with regard to the processing of personal data. According to such legislation, patients will be able to exert their rights to access, modification, opposition and cancellation of their data, for which the clinical trial physician must be addressed. The content of the CRFs, as well as the documents generated during the study will be considered strictly confidential and not revealed to third parties.

## **12.10. Documentation**

The Investigator/Institution should maintain trial documents according to ICH Topic E6 Section 8, and as required by pertinent regulatory requirements.

Essential documents should be stored according to ICG GCP guidelines or for a longer period of time, if required by pertinent regulations.

The original patient data (clinical record) must be kept archived for the time stipulated by the study centre regulations. This period should not be less than 15 years.

## 13. TRANSLATIONAL STUDY

### PRIMARY OBJECTIVES:

- To evaluate the influence of the angiogenic status of the tumor on the response to Pazopanib.
- To evaluate the serum profile of serum cytokine markers as indicator of response to Pazopanib.

### SECONDARY OBJECTIVES:

- To evaluate microvessel density (MVD) and p53, MDM2, PTEN and VEGF/PDGF pathways by IHQ expression and their correlation with prognosis as well as their role as predictive factors to treatment with Pazopanib (Response, PFS and OS).
- To evaluate serum levels of several angiogenic factors/cytoquines using Luminex XMAP Technology at baseline, after the first 3 weeks of treatment, at maximum response and at progression and their predictive value for survival and response to treatment: VEGF-A, PIGF-1, SDF-1 alpha (CXCL12), TNF alpha, IL-8, IL-6, PDGF –beta, HGF, E- Selectine, ICAM1, MMP-9 and FGFb.
- To analyse PIK3CA mutations in order to demonstrate if those liposarcomas with PIK3CA mutations defines a subgroup of patients with differential response to Pazopanib.

### STUDY OF BIOMARKERS:

Paraffin-embedded samples from 74 original tumors and if clinically acceptable (ex. superficial or easily accessible locations), tumour biopsy at study entry will be collected and the following analysis will be carried out:

- Microvessel density on full sections of the tissue.
- Immunohistochemical profile of angiogenic markers and p53, MDM2 and PTEN.
- Quantitative RT-PCR of a panel of angiogenic markers.

Serum from peripheral blood will be performed (4 per subject):

1. Within 72 hours prior starting the treatment (basal).
2. Within 72 hours after the first 3 weeks of treatment.
3. Within 72 hours after radiological response is documented.
4. Within 72 hours after progressive disease is documented.

Methodology:

a) Microvessel density and immunohistochemistry: Full sections of paraffin-embedded material will be stained with anti-CD34 or anti-CD31 and evaluated using a light microscope and specific software for measuring microvessels with no muscular walls.

Tissue microarrays (TMA) will be constructed containing at least two cores (1.0 mm in diameter) from each tissue sample.

At least the following antibodies will be tested: VEGF, PDGF, VEGFR-1 (flt-1), VEGFR-2 (flk-1/KDR), PDGFR-alfa, PDGFR-beta, HIF-1, TSP-1, VE-cadherin, p53, MDM2 and PTEN.

Additional tests could be considered depending of new findings or evidences in the field of tumor angiogenesis.

b) RT-PCR Low density arrays for the expression of angiogenic factors: We will perform an RNA extraction from paraffin embedded material and an RT-PCR low density expression array containing 94 angiogenesis-related genes will be analysed. These arrays include known angiogenesis growth factors like VEGF, and known matrix derived inhibitors such as endostatin. Additionally, the panel contains markers and targets for angiogenesis and lymphangiogenesis.

List of genes included:

- Angiogenic growth factors (28): ANG, ANGPT1, ANGPT2, ANGPT4, CSF3, CTGF, CXCL12, ECGF1, EDIL3, EPHB2, FGF1, FGF2, FGF4, FST, GRN, HGF, IL8, LEP, MDK, PDGFB, PROK1, PTN, TGFA, TGFB1, TNF, VEGF, VEGFB, VEGFC.
- Angiogenesis inhibitors (37): ADAMTS1, ANGPTL1, BAI1, CHGA, COL15A1, COL18A1, COL4A1, COL4A2, COL4A3, CXCL10, CXCL2, F2, FBLN5, FGA, FLT1, FN1, HSPG2, IFNB1, IFNG, IL12A, ITGA4, LECT1, PF4, PLG, PRL, SEMA3F, SERPINB5, SERPINC1, SERPINF1, THBS1, THBS2, TIMP2, TIMP3, TNFSF15, TNMD, TNNI1, VASH1.
- Angiogenesis markers (10): AMOT, ANGPTL2, ANGPTL3, ANGPTL4, CEACAM1, HEY1, ITGAV, PECAM1, PGK1, XLKD1.
- Angiogenesis targets (13): EDG1, ENPP2, FLT3, FLT4, ITGB3, KDR, KIT, NRP1, NRP2, PDGFRA, PDGFRB, TEK, TIE1
- Lymphangiogenesis markers (5): CD44, CDH5, FIGF, FOXC2, PROX1
- Controls (2): 18S, GAPDH

c) Serum cytokine markers: The Luminex technology will be employed for the analysis of 12 cytokines [VEGF-A, PlGF-1, SDF-1 alpha (CXCL12), TNF alpha, IL-8, IL-6, PDGF-beta, HGF, E-Selectine, ICAM1, MMP-9 and FGFb].

d) Analysis of PIK3CA mutations: DNA extraction, amplification of exons 4, 7, 9 and 20 of PIK3CA by PCR and direct sequencing will be performed.

[figure not shown]
The proposed biomarker study includes analysis of tumor tissue at diagnosis and serum cytokines and growth factors at different phases within the treatment schedule. In the case of serum, the kinetic profile of each biomarker will be considered (decreased, constant, increased). All analysed parameters will be correlated with: Progression-free survival (PFS) assessed 12 weeks after start of treatment (According the RECIST criteria 1.1); median PFS; objective tumor response; overall survival and histopathological parameters. For the statistical analysis, we will use binary variables reflecting the positivity status of the measures (yes or no; presence/absence). Association with histopathological parameters, and objective tumor response, all categorical, will be also assessed using a chi-square test to determine homogeneity or linear trend for ordinal variables. The significance level will be set at 5%. To study the impact of the histological, immunohistochemical and molecular factors on progression-free survival (PFS) and overall survival (OS), the Kaplan-Meier proportional risk test (log rank) will be used. Evidence of the relative risk for each patient will be also provided by means of a Cox proportional hazards model using stepwise selection to identify the independent predictors of poor outcome.

We do not plan to use multivariate analysis to analyse biomarkers. Standard pre-post univariate tests will be used instead.

For the kinetic profile of the serum biomarkers, each variable will be considered as continuous. A correlation between the growth factor or cytokine levels with the different points of the treatment schedule will be considered and the slope value will be used in

order to distinguish those cases with no change, negative or positive trend. The threshold will be calculated after considering the behaviour of the whole series. The slope value will be considered from baseline and using the nonparametric Wilcoxon signed-rank test. However other analysis will be undertaken depending of the behaviour of the measures.

For sending the biological samples, please contact to:

An additional document will be provided in the Investigator Site File with detailed biological sample collection and shipment procedures.

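### Section 13 codes quantitative biomarkers as positive or negative with no cut-point; analyse microvessel density, RT-PCR expression and baseline serum levels as continuous variables instead.

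*Protocol*

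**What the plan says.** Protocol section 13 (Study of biomarkers) describes several measures that yield quantities:

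- Vessel sections are "evaluated using a light microscope and specific software for measuring microvessels with no muscular walls".
- Tumour RNA goes to "Quantitative RT-PCR of a panel of angiogenic markers".
- Twelve serum cytokines are assayed by Luminex.

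All parameters are to be related to 12-week PFS, median PFS, objective response, overall survival and histopathology. The coding rule follows directly: "For the statistical analysis, we will use binary variables reflecting the positivity status of the measures (yes or no; presence/absence". The named methods are chi-square tests (homogeneity, or linear trend for ordinal variables), log-rank and Cox models, at a 5% level. No cut-point is stated for any marker.

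Serum has one exception: "For the kinetic profile of the serum biomarkers, each variable will be considered as continuous". The profile is nevertheless reported in three groups: "In the case of serum, the kinetic profile of each biomarker will be considered (decreased, constant, increased". The boundary between the groups is left to the data: "The threshold will be calculated after considering the behaviour of the whole series". The test named for the slope is the Wilcoxon signed-rank: "The slope value will be considered from baseline and using the nonparametric Wilcoxon signed-rank test". A closing clause leaves room for more: "However other analysis will be undertaken depending of the behaviour of the measures".

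The secondary translational objectives (Protocol sections 4.3.3 and 13) ask whether serum levels, at baseline among other times, predict survival and response. SAP section 1.16.3 repeats the translational objectives, but the SAP sections available give no analysis of them. Section 13 of the Protocol is therefore the governing text.

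**The concern.** Yes/no coding suits a mutation, and it suits a stain that the pathologist scores as positive or negative. It does not suit a vessel density, a normalised expression value or a serum concentration, where patients differ by degree.

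Both primary translational objectives (the tumour's angiogenic status and the serum cytokine profile as indicators of response) draw on such measures. With at most 74 patients, and 37 in a cohort, information given away in coding cannot be recovered by enrolling more. A true association is then more easily missed, and a non-significant result may be read as absence of one.

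The wording is also unclear about what positive means. It could mean detected or it could mean above some level, and the plan does not say which, or what level.

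**Working it through.** **No figure to reproduce.** Section 13 states no power, effect size or expected share of positive patients, so the plan has no number of its own on this point. The size has to be shown under assumptions.

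**Which measures the binary rule reaches**

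| Measure | Nature of the data | Continuous analysis restored later in section 13? |
|---|---|---|
| Microvessel density | software-measured quantity | no |
| RT-PCR expression | quantitative | no |
| Serum level at one time (e.g. baseline) against outcome | concentration | no |
| Serum change over time | slope | yes, then cut into three groups |
| PIK3CA mutation | present or absent | not needed |
| Immunohistochemistry | depends on the scoring, not stated | not needed if scored yes/no |

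The Wilcoxon signed-rank test on the serum slope asks whether levels move from baseline. It does not relate a level, or a change, to response, PFS or survival. It therefore leaves the third row under the binary rule.

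**Information kept after dichotomising**

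Inputs: N = 74 tumours (section 13), the maximum of 37 per cohort (section 10.4). Assumptions: a normally distributed marker, linearly related to outcome, cut so that the larger group has share q.

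Formula: E = φ(z_q)² / [q(1 − q)], with z_q the standard normal quantile and φ the normal density. The effective number is 74 × E.

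- q = 0.50: z = 0, φ = 0.3989; E = 0.1592 / 0.25 = 0.637; 74 × 0.637 = 47
- q = 0.75: z = 0.6745, φ = 0.3178; E = 0.1010 / 0.1875 = 0.539; 74 × 0.539 = 40
- q = 0.90: z = 1.2816, φ = 0.1755; E = 0.0308 / 0.09 = 0.342; 74 × 0.342 = 25

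E falls below one half only when the larger group exceeds about 79%. If every sample is positive, the variable has no variance and neither a chi-square nor a log-rank test exists.

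**What that does to power**

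Power ≈ Φ[atanh(ρ√E) × √(N − 3) − 1.96], two-sided 5% (the plan does not state sidedness), with E = 1 for the uncut marker. The correlation ρ is assumed.

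| N | ρ | Continuous | 50/50 | 75/25 | 90/10 |
|---|---|---|---|---|---|
| 74 | 0.3 | 74% | 54% | 47% | 32% |
| 74 | 0.4 | 95% | 80% | 72% | 52% |
| 74 | 0.5 | 99.6% | 95% | 90% | 72% |
| 37 | 0.4 | 70% | 49% | 42% | 28% |

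Worked line (N = 74, ρ = 0.4, 50/50): 0.4 × 0.798 = 0.319; atanh = 0.331; 0.331 × √71 = 2.79; 2.79 − 1.96 = 0.83; Φ(0.83) = 0.80.

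**The case against.** The best case for the plan has four parts.

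- **Serum is not simply reduced to presence or absence.** This stands. Section 13 treats the serum time-course as continuous, so a reader who infers that all the Luminex data are binary goes too far. The binary rule reaches only single-time serum levels related to outcome.
- **The loss need not be most of the information.** This stands. A median split keeps 64%, and the loss passes one half only beyond roughly 79/21. The documents give no positive shares, so a general claim that most is lost is unsupported.
- **Positive may mean above a level.** This stands in part. A marker present in everyone can still be split at a level, so a reader should not conclude that such markers leave nothing to test. That conclusion needs the literal detection reading and detection rates that the documents do not give. However, the reading that avoids it needs a level, and none is stated.
- **A cut chosen from the marker data alone does not inflate error.** This stands. The one data-driven threshold, for the serum slope, follows the behaviour of the series; outcome is not mentioned. A simulation of cuts set without regard to outcome (n = 74, assumed 30% success, 20,000 runs) gave chi-square error rates of about 5.1%, 4.9% and 4.4% at the median, 75th and 90th percentiles. A reader might infer from serum being shipped only at the end of the study (Protocol section 8.2, item 12) that cuts will be tuned to known outcomes. The timing makes that possible, but no section proposes it.

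The closing clause on other analyses leaves a route to continuous methods but commits nobody to them.

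**Conclusion.** The point holds in limited form. Section 13 sets a binary rule, without cut-points, for microvessel density, RT-PCR expression and single-time serum levels, all of which are measured as quantities. Nothing later restores a continuous analysis for them. The serum kinetic profile is the exception, and its three-group threshold is not fixed in advance.

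Even the most favourable split gives up about 36% of the information. At an assumed correlation of 0.4 and the full 74 patients, power falls from about 95% to 80% at a median split and to 52% at 90/10. These sizes rest on a normal marker, a linear relation and assumed splits. The number 74 is a ceiling, since either cohort may stop after 17 patients (Protocol section 10.4).

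This is a cheap and worthwhile improvement to the correlative sub-study. It does not touch the 12-week PFS endpoint, the other clinical endpoints or the two-stage stopping rule.

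**What to change.** Replace the coding sentence in Protocol section 13 with the following rules, and carry them into the translational analysis programs:

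- **Continuous markers.** Analyse microvessel density, RT-PCR expression normalised to the listed controls (18S, GAPDH) and baseline serum levels as continuous variables. Use the log scale where skewed, and state a rule for values below detection.
- **Models.** Use logistic models for 12-week PFS and response, and Cox models for PFS and OS.
- **Serum change.** If the day-22 to baseline ratio is related to PFS or OS, time these from a day-22 landmark among patients still at risk. The ratio does not exist at treatment start, from which sections 10.1.2 and 10.4 time both endpoints.
- **Yes/no coding.** Keep it for PIK3CA mutation and for immunohistochemistry scored that way. If any other marker must be split, state one cut-point for it in advance.
- **Serum no-change band.** Fix it, for instance from assay reproducibility, before marker data are linked to outcome.

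The cost is wording and programming, with no new samples or assays. The downside is that effects are reported per doubling, or per unit, rather than as a contrast of positive with negative patients.
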